2.2. Primary and Secondary Measures and Endpoints

2.2.1. Primary Efficacy Endpoint

The primary efficacy endpoint is the mean change from baseline (28-day run-in period) in the monthly average number of headache days of at least moderate severity during the 12-week period after the 1st dose of study drug.

2.2.2. Secondary Efficacy Endpoints

The secondary efficacy endpoints are as follows:

- mean change from baseline (28-day run-in period) in the monthly average number of migraine days during the 12-week period after the 1st dose of study drug
- proportion of patients reaching at least 50% reduction in the monthly average number of headache days of at least moderate severity during the 12-week period after the 1st dose of study drug
- mean change from baseline (28-day run-in period) in the monthly average number of days of use of any acute headache medications during the 12-week period after the 1st dose of study drug
- mean change from baseline (28-day run-in period) in the number of headache days of at least moderate severity during the 4-week period after the 1st dose of study drug
- mean change from baseline (28-day run-in period) in the monthly average number of headache days of at least moderate severity during the 12-week period after the 1st dose of study drug in patients not receiving concomitant migraine preventive medications
- mean change from baseline (day 0) in disability score, as measured by the HIT-6 at 4 weeks after administration of the last (3rd) dose of study drug

2.2.3. Exploratory Efficacy Endpoints

The exploratory efficacy endpoints are as follows:

- mean change from baseline (28-day run-in period) in the weekly number of headache days of at least moderate severity during the 4-week period after the 1st dose of study drug
- proportion of patients reaching at least 75% reduction and total (100%) reduction in the monthly average number of headache days of at least moderate severity during the 12-week period after the 1st dose of study drug
- proportion of patients reaching at least 50% reduction and at least 75% reduction in the number of headache days of at least moderate severity during the 4-week period after the 1st dose of study drug for whom this level of effect is sustained throughout the 12-week period after the 1st dose of study drug

- mean change from baseline (28-day run-in period) in the monthly average number of headache days of at least moderate severity during the 12-week period after the 1st dose of study drug in patients who used topiramate for migraine in the past
- mean change from baseline (28-day run-in period) in the monthly average number of headache days of at least moderate severity during the 12-week period after the 1st dose of study drug in patients who used onabotulinumtoxinA for migraine in the past
- mean change from baseline (28-day run-in period) in the monthly average number of headache days of at least moderate severity during the 4-week period after the 2nd dose of study drug
- mean change from baseline (28-day run-in period) in the monthly average number of headache days of at least moderate severity during the 4-week period after the last (3rd) dose of study drug
- mean change from baseline (28-day run-in period) in the monthly average number of headache days of any severity during the 12-week period after the 1st dose of study drug
- mean change from baseline (28-day run-in period) in the monthly average number of migraine days during the 4-week period after each dose of study drug
- mean change from baseline (28-day run-in period) in the weekly number of migraine days during the 4-week period after the 1st dose of study drug
- proportion of patients reaching at least 50% reduction, at least 75% reduction, and total (100%) reduction in the monthly average number of migraine days during the 12-week period after the 1st dose of study drug
- proportion of patients reaching at least 50% reduction and at least 75% reduction in the number of migraine days during the 4-week period after the 1st dose of study drug for whom this level of effect is sustained throughout the 12-week period after the 1st dose of study drug
- mean change from baseline (28-day run-in period) in the number of migraine days during the 12-week period after the 1st dose of study drug for patients not receiving concomitant preventive migraine medications
- mean change from baseline (28-day run-in period) in the number of migraine days during the 12-week period after the 1st dose of study drug for patients who used topiramate for migraine in the past
- mean change from baseline (28-day run-in period) in the number of migraine days during the 12-week period after the 1st dose of study drug for patients who used onabotulinumtoxinA for migraine in the past
- mean change from baseline (28-day run-in period) in the monthly average number of headache hours of any severity during the 12-week period after the 1st dose of study drug

- mean change from baseline (28-day run-in period) in the monthly average number of headache hours of at least moderate severity during the 12-week period after the 1st dose of study drug
- mean change from baseline (28-day run-in period) in the monthly average number of days of use of migraine-specific acute headache medications (triptans and ergot compounds) during the 12-week period after the 1st dose of study drug
- mean change from baseline (28-day run-in period) in the monthly average number of days with nausea or vomiting during the 12-week period after the 1st dose of the study
- mean change from baseline (28-day run-in period) in the monthly average number of days with photophobia and phonophobia during the 12-week period after the 1st dose of study drug
- mean change from baseline (day 0) in quality of life, as measured by the MSQOL questionnaire, at 4 weeks after administration of the last (3rd) dose of study drug
- mean change from baseline (day 0) in the health status, as measured by EQ-5D-5L questionnaire, at 4 weeks after administration of the last (3rd) dose of study drug
- mean change from baseline (day 0) in patient depression status, as measured by the PHQ-2 and the PHQ-9, at 4 weeks after administration of the last (3rd) dose of study drug
- mean change from baseline (day 0) in patient work productivity and activity impairment, as measured by the WPAI questionnaire, at 4 weeks after administration of the last (3rd) dose of study drug
- assessment of patient satisfaction, as measured by the PGIC scale, at 4 weeks after administration of the 1st dose of study drug, at 4 weeks after administration of the 2nd dose of study drug, and at 4 weeks after administration of the last (3rd) dose of study drug

2.2.4. Safety and Tolerability Endpoints

The safety and tolerability endpoints for this study are as follows:

- occurrence of adverse events throughout the study
- abnormal standard 12-lead electrocardiogram (ECG) findings
- changes from baseline in vital signs (systolic and diastolic blood pressure, pulse, oral temperature, and respiratory rate) measurements
- changes from baseline in clinical laboratory (serum chemistry, hematology, coagulation, and urinalysis) test results
- abnormal physical examination findings
- abnormal local injection site tolerability findings (i.e., erythema, induration, ecchymosis) and occurrence of injection site pain

- suicidal ideation and behavior as suggested by the electronic Columbia-Suicide Severity Rating Scale (eC-SSRS)

2.2.5. Pharmacokinetic/Immunogenicity/Biomarker Endpoints

2.2.5.1. Pharmacokinetic Endpoints

There are no prespecified pharmacokinetic endpoints.

2.2.5.2. Immunogenicity Endpoint

There are no prespecified immunogenicity endpoints.

2.2.5.3. Biomarker Endpoints

The biomarker assessments and endpoints will be provided in a separate document by Personal Medicine and Pharmacogenomics.

2.3. Sample Size and Power Considerations

In a Phase 2b study in CM patients, a treatment difference of 1.7 days of monthly average headache days of at least moderate severity between the TEV-48125 675/225/225 mg and placebo treatment groups was observed. A sample size of 867 patients (i.e., 289 evaluable patients completing the study per treatment group) results in at least 90% power for the study to succeed (assuming a common standard deviation [SD] of 6.29 days) at an alpha level of 0.05. Assuming a 15% discontinuation rate, 340 patients per treatment group will be randomized.

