1. STUDY OBJECTIVES

1.1. Primary Objectives

The primary objectives of this study are as follows:

- to demonstrate the efficacy of 2 dose regimens of TEV-48125, as assessed by the decrease in the monthly average number of headache days of at least moderate severity during the 12-week period after the 1st dose of study drug relative to the baseline period
- to evaluate the safety and tolerability 2 dose regimens of TEV-48125 in the preventive treatment of CM

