3.3. Full Analysis Set

The full analysis set (FAS) will include all patients in the ITT population who receive at least 1 dose of study drug and have at least 10 days of post baseline efficacy assessments on the primary endpoint. The FAS will be used for all efficacy analysis.

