4.4. Multiple Comparisons and Multiplicity

A fixed-sequence (hierarchical) testing procedure will be implemented to control the type 1 error rate at 0.05. The sequence of comparisons will be as follows:

1. mean change from baseline (28-day run-in period) in the monthly average number of headache days of at least moderate severity during the 12-week period after the 1st dose of study drug for the TEV 48125 675/225/225 mg treatment group versus the placebo treatment group
2. mean change from baseline (28-day run-in period) in the monthly average number of migraine days during the 12-week period after the 1st dose of study drug for the TEV 48125 675/225/225 mg treatment group versus the placebo treatment group
3. mean change from baseline (28-day run-in period) in the number of headache days of at least moderate severity during the 4-week period after the 1st dose of study drug for the TEV 48125 675/225/225 mg and TEV 48125 675 mg/placebo/placebo treatment group versus the placebo treatment group
4. proportion of patients reaching at least 50% reduction in the monthly average number of headache days of at least moderate severity during the 12-week period after the 1st dose of study drug for the TEV 48125 675/225/225 mg treatment group versus the placebo treatment group
5. mean change from baseline (28-day run-in period) in the monthly average number of headache days of at least moderate severity during the 12-week period after the 1st dose of study drug for the TEV 48125 675 mg/placebo/placebo treatment group versus the placebo treatment group
6. mean change from baseline (28-day run-in period) in the monthly average number of days of use of any acute headache medications during the 12-week period after the 1st dose of study drug for the TEV 48125 675/225/225 mg treatment group versus the placebo treatment group

7. proportion of patients reaching at least 50% reduction in the monthly average number of headache days of at least moderate severity during the 12-week period after the 1st dose of study drug for the TEV 48125 675 mg/placebo/placebo treatment group versus the placebo treatment group
8. mean change from baseline (28-day run-in period) in the monthly average number of days of use of any acute headache medications during the 12-week period after the 1st dose of study drug for the TEV 48125 675 mg/placebo/placebo treatment group versus the placebo treatment group

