9. mean change from baseline (28-day run-in period) in the monthly average number of migraine days during the 12-week period after the 1st dose of study drug for the TEV 48125 675 mg/placebo/placebo treatment group versus the placebo treatment group
10. mean change from baseline (28-day run-in period) in the monthly average number of headache days of at least moderate severity during the 12-week period after the 1st dose of study drug for the TEV 48125 675/225/225 mg treatment group versus the placebo treatment group in patients not receiving concomitant migraine preventive medications
11. mean change from baseline (28-day run-in period) in the monthly average number of headache days of at least moderate severity during the 12-week period after the 1st dose of study drug for the TEV 48125 675 mg/placebo/placebo treatment group versus the placebo treatment group in patients not receiving concomitant migraine preventive medications
12. mean change from baseline (day 0) in disability score, as measured by the HIT-6 at 4 weeks after administration of the last (3rd) dose of study drug for the TEV 48125 675/225/225 mg treatment group versus the placebo treatment group
13. mean change from baseline (day 0) in disability score, as measured by the HIT-6 at 4 weeks after administration of the last (3rd) dose of study drug for the TEV 48125 675 mg/placebo/placebo treatment group versus the placebo treatment group

If the resulting 2-sided p-value from the first comparison is ≤ 0.05 , then the next comparison of interest will be interpreted inferentially at the alpha level of 0.05. This process will continue either until all comparisons of interest are interpreted inferentially or until the point at which the resulting 2-sided p value for a comparison of interest is >0.05 . At the point where $p > 0.05$, no further comparisons will be interpreted inferentially.

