6.2.2. Primary Analysis

The hypothesis testing for the primary analysis is:

$$H_o : \delta_1 = \delta_2 \quad vs \quad H_a : \delta_1 \neq \delta_2$$

where δ_1 and δ_2 are the estimates of mean change from baseline in the monthly average number of headache days of at least moderate severity for the TEV-48125 treatment group and the placebo group respectively. The estimated difference of TEV-48125 675/225/225 mg versus the placebo and TEV-48125 675/placebo/placebo mg versus the placebo will be tested following the pre-specified fixed sequence as described in Section 4.4.

An analysis of covariance (ANCOVA) method will be applied for the primary analysis. The model will include treatment, sex, region (Table 2), and baseline preventive migraine medication use (yes/no) as fixed effects; the baseline number of headache days of at least moderate severity and years since onset of migraines as covariates. The least square (LS) means for the treatment groups, LS means and corresponding 95% confidence intervals for the treatment differences (TEV-48125 – placebo), and associated p-values will be provided.

The following sample SAS code pertains to the primary analysis.

```
ODS OUTPUT DIFFS=XXX LSMEANS=XXX TESTS3=XXX;
PROC MIXED DATA=XXX;
    CLASS TREAT SEX BMU REGION;
    MODEL CHG=BASE YOD BMU SEX TREAT REGION/S;
    LSMEANS TREAT/PDIFF CL ALPHA=0.05;
RUN;
```

The normality of the residuals from the ANCOVA model will be checked using Shapiro Wilk's normality test. In case that the Shapiro Wilk's test has a p value ≤ 0.01 , Wilcoxon rank-sum test will be conducted as the primary analysis using SAS procedure NPAR1WAY for each active treatment group and placebo group. P value based on normal approximation from this procedure will be selected for the treatment comparison. The ANCOVA analysis will be performed as a supportive analysis.

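### Does SAP Section 2.3 overstate power by giving 90% for the study to succeed when the primary objective names two regimens?

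*SAP*

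**What the plan says.** Section 2.3 bases the sample size on a Phase 2b result, "a treatment difference of 1.7 days of monthly average headache days of at least moderate severity between the TEV-48125 675/225/225 mg and placebo treatment groups". It then says that 867 patients, 289 evaluable per group, "results in at least 90% power for the study to succeed (assuming a common standard deviation [SD] of 6.29 days"), at alpha 0.05. Allowing for 15% discontinuation, 340 per group are randomised. The section does not define success and gives no effect or power for 675 mg/placebo/placebo.

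Three other places bear on what success might mean:

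- Section 1.1 states the primary objective, for headaches of moderate or worse severity, as "to demonstrate the efficacy of 2 dose regimens of TEV-48125, as assessed by the decrease in the monthly average number of headache days".
- Section 6.2.2 says that the differences for "TEV-48125 675/225/225 mg versus the placebo and TEV-48125 675/placebo/placebo mg versus the placebo will be tested" in the order fixed by Section 4.4.
- Section 4.4 puts the primary endpoint for 675/225/225 mg at step 1 and for 675 mg/placebo/placebo at step 5. Steps 2 to 4 are migraine days (675/225/225 mg), the 4-week comparison (both active groups against placebo) and 50% responders (675/225/225 mg). After the first p-value above 0.05, "no further comparisons will be interpreted inferentially".

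**The concern.** Read beside Section 1.1, a power for the study as a whole seems to cover the whole primary objective, which is efficacy of both regimens. The calculation covers only one of them. The second regimen's primary-endpoint test comes fifth, behind three secondary comparisons, and supports no inferential claim if any of the first four fails. A reader could therefore believe that the two-regimen objective is powered at 90% when the joint power is lower, and could give too much weight to a missed or unreached step 5 as evidence against the 675 mg/placebo/placebo regimen.

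**Working it through.** **Inputs.** From Section 2.3: difference 1.7 days (675/225/225 mg against placebo), common SD 6.29 days, 289 evaluable per group, alpha 0.05, 15% discontinuation. From Section 4.4: two-sided tests. From Section 2.1: 1:1:1 allocation. The effect of 675 mg/placebo/placebo is not given and is varied below as an assumption.

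**Step 1: reproduce the plan's figures.**

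- Standard error of a pairwise difference: 6.29 × √(2/289) = 0.523 days.
- Standardised effect: 1.7 / 0.523 = 3.249.
- Power, normal approximation: Φ(3.249 − 1.960) = Φ(1.289) = 90.1%.
- Power, noncentral t with 576 degrees of freedom: 90.0%.
- Totals: 289 × 3 = 867, and 289 / 0.85 = 340.

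Every figure in Section 2.3 is reproduced. The 90% is the power of one pairwise contrast, comparison 1 of Section 4.4.

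**Step 2: power for both regimens on the primary endpoint.** The two contrasts share the placebo arm. With equal arms their correlation is (σ²/n) / (2σ²/n) = 0.5. Joint power is the probability that both standardised differences exceed 1.960 under a bivariate normal with that correlation, holding the first effect at 1.7 days.

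| Assumed effect of 675 mg/placebo/placebo (days) | Its own pairwise power, 289 per arm | Both regimens, 289 per arm | Both regimens, 340 per arm |
|---|---|---|---|
| 1.0 | 48.1% | 46.6% | not computed |
| 1.3 | 70.0% | 66.6% | 74.6% |
| 1.5 | 81.8% | 76.7% | 84.1% |
| 1.7 | 90.1% | 83.4% | 89.8% |
| 2.0 | 96.9% | 88.3% | not computed |
| 2.5 | 99.8% | 90.0% | not computed |

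A simulation with pooled-variance t tests (400,000 runs, 289 per arm, equal effects) also gives 83.4% for both.

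The 340 column is an upper bound on numbers. It applies if everyone randomised is analysed, which is approached because Section 3.3 keeps treated patients who "have at least 10 days of post baseline efficacy assessments on the primary endpoint", whether or not they complete.

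**Step 3: what does not depend on the assumption.** The probability of winning both contrasts cannot exceed the probability of winning the first, so joint power at 289 per arm is at most 90.1% whatever the second effect is. Steps 2 to 4 stand in front of step 5 and can only lower it. The direction is certain. The size is not, because it rests on an effect the SAP does not state.

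**Step 4: which reading the text supports.** The sentence before the power statement names one contrast and one effect, and no other effect in Section 2.3 could produce 90%. That contrast is also the first gate in Section 4.4, and if it fails nothing later can be claimed. Section 1.1 states an objective and Section 6.2.2 lists what is tested in sequence. Neither says that the study succeeds only if both regimens win. Taking success as comparison 1 fits every number in the section.

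**The case for a change.** The strongest case for a change is that the label is wider than the calculation. The SAP names two regimens in its primary objective, tests both in its primary analysis, and attaches the word study to a power belonging to one contrast with about 0.1 point to spare. At 289 per arm, the basis on which Section 2.3 makes its claim, joint power falls short of 90% unless the second effect is about 2.5 days or more, well above the 1.7 days cited for the other regimen. The remedy would be a few words.

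Two parts of this stand: the phrase is undefined, and joint power is lower than 90% for any plausible second effect at 289 per arm. Neither shows an error. Powering a fixed sequence on its first test is ordinary practice, and the text identifies that test. Putting a joint figure such as 83% into the SAP would add a number that depends on an equal effect the plan does not assume, on ignoring steps 2 to 4, and on 289 rather than a larger analysed number.

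Covariate adjustment adds to the uncertainty. About 343 evaluable per arm would give 90% on both at equal effects. At 289 per arm the same power needs an SD of 6.29 × √(289/343) ≈ 5.77, meaning covariates that explain 1 − 289/343 ≈ 16% of the variance. The SAP does not say whether 6.29 is already an adjusted SD.

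The loss of a claim for the second regimen after an earlier failure comes from the testing order in Section 4.4, not from the wording of Section 2.3.

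**Conclusion.** No change to the plan follows. The 90% is correct for comparison 1 of Section 4.4 (1.7 days, SD 6.29, 289 per arm, two-sided 0.05: 90.0% to 90.1%), and Section 2.3 names that contrast immediately before stating the power. The phrase about the study succeeding is loose and should not be read as power for both regimens. On that reading the value would be at most 90.1%, and about 83% under an assumed equal 1.7-day effect with 289 per arm and the gates at steps 2 to 4 ignored, falling to 66.6% at 1.3 days. Those joint figures rest on an effect for 675 mg/placebo/placebo that the SAP does not give.

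A planning power statement enters no p-value, estimate or claim. Rewording it would leave the sample size, testing order, error rate and all analyses as they are. Anyone interpreting a failed or unreached step 5 can read the limitation from Sections 2.3 and 4.4 together.

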2.4. Randomization and Blinding

2.4.1. Randomization

Patient randomization codes will be maintained in a secure location within Teva Clinical Supply Chain. At the time of analysis, when treatment codes are needed, the Teva statistician assigned to the study will make a request to unblind and will receive the unblinded codes.

2.4.2. Blinding/Unblinding

This is a randomized study with stratification based on sex, country, and baseline preventive migraine medication use (yes, no). Each patient will undergo randomization in a 1:1:1 ratio within the stratum to which he or she belongs to receive 1 of the 2 TEV 48125 dose regimens or placebo, as assigned by the IRT. The IRT will manage initial drug supply, maintenance of adequate study drug supplies on site, and study randomization centrally. At the time of each study visit, the IRT will be queried, and site personnel will retrieve and administer a 1.5 mL volume from each syringe contained in the appropriately numbered kit(s).

The sponsor, investigators, study staff (except for staff involved in bioanalytical analyses), and patients will be blinded to treatment assignment. A computer-generated master randomization list will be provided to drug packaging facilities. Packaging vendor(s) will package active drug and placebo into single-visit kits according to Good Manufacturing Practice procedures. Kits will be identical in appearance and contain 1 prefilled syringe with active drug or placebo. Adequate

kit supply for upcoming study visits will be managed by IRT and kept (refrigerated at 2°C to 8°C) on site.

In case of a serious adverse event or pregnancy, or in cases when knowledge of the study drug assignment is needed to make treatment decisions, the investigator may unblind the patient's drug assignment as deemed necessary, mainly in emergency situations. Individual treatment codes, indicating the treatment randomization for each randomized patient, will be available to the investigator(s) and/or pharmacist(s) at the study center via the IRT, both via telephone and internet. If possible, the sponsor should be notified of the event prior to breaking of the code. If this is not possible, the sponsor should be notified immediately afterwards, and the patient's drug code assignment should not be revealed. Breaking of the treatment code can always be performed by the site without prior approval by the sponsor.

When a blind is broken, the patient will be withdrawn from the study, and the event will be recorded onto the CRF. The circumstances leading to the breaking of the code should be fully documented in the investigator's study files and in the patient's source documentation. Treatment assignment should not be recorded in any study documents or source document.

In blinded studies, for adverse events that are defined as: suspected, unexpected, serious, adverse reaction (SUSAR) (i.e., reasonable possibility; see protocol Section 7.1.4), Global Patient Safety and Pharmacovigilance may independently request that the treatment code be revealed (on a case by case basis) to comply with regulatory requirements. The report will be provided in an unblinded manner for regulatory submission. If this occurs, blinding will be maintained for the investigator and for other personnel involved in the conduct, analysis, and reporting of the data.

